#### **4.5.3 Exploratory Efficacy Endpoints**

All bleeds will be characterized descriptively, including the type, location, and cause of bleed (surgery/procedure, traumatic, spontaneous). Bleed rates for spontaneous and traumatic bleeds will be calculated.

For EQ-5D-5L, Haem-A-QoL, and Haemo-QoL-SF, exploratory analyses include descriptive analyses of change from baseline and between group comparisons over time for each individual subscale and the overall score. In addition, a paired t-test will be conducted to compare the 24-week with the baseline score for the EQ-5D-5L and Haem-A-QoL questionnaires by treatment arm separately. Due to the limited number of adolescent patients, paired t-tests will not be conducted on the Haemo-QoL-SF scales. For EQ-5D-5L and Haem-A-QoL, the number of patients who reported a clinically meaningful change from baseline to Week 24 will be reported. For EQ-VAS, a meaningful change is 7 points and for the index scale it is 0.07 points (Walters et al. 2005; Pickard et al. 2007). For Haem-A-QoL a meaningful change is 7 points for the total score and 10 points for the physical health score (Wyrwich et al. 2015).

The number of days away from school/work and days hospitalized will be presented by treatment arm using descriptive statistics and 95% CIs.

[REDACTED]

[REDACTED]

Regarding the preference survey that is given to patients in Arms A, B, and D at Week 17, the proportion of patients preferring the older hemophilia IV treatment prior to enrollment in the study, emicizumab, and without treatment preference will be computed along with 95% CIs. For patients who have a preference to emicizumab, the factors influencing the preference will be treated like ordered categorical variables (e.g., from “had no influence in my treatment preference” to “was the most important factor in my treatment preference”) and will be summarized accordingly. The same approach will be applied for patients who have a preference to the old hemophilia treatment. Bar charts by preference factors may be produced to characterize the preference profile of each treatment (“emicizumab” or “old hemophilia treatment”).

[REDACTED]

[REDACTED]

[REDACTED]

[REDACTED]

[REDACTED]

#### **4.5.4 Sensitivity Analyses**

The sensitivity analyses will include different methods to define bleeds or eligible bleed data and different statistical models.

Different ways to define bleeds or eligible bleed data for A versus C and B versus C randomized comparisons:

- Include all bleeds recorded by patients in the electronic patient-reported outcomes device (i.e., without the 72-hour rule)
- Include treated joint bleeds defined as treated bleeds where the bleed type is “joint,” regardless whether any symptoms have been observed
- Include only patients who received at least 12 weeks of emicizumab treatment (if needed)
- Count days when treatment for bleeds was administered instead of the bleeds themselves
- Include only the first 24 weeks of efficacy period in the analysis. Patients who withdraw from study treatment are included up to the point of study treatment withdrawal.

Different ways to analyze secondary endpoints with intra-patient comparison:

- D intra-patient: include also period after up-titration
- A intra-patient and B intra-patient: provide also analyses separately by arm (i.e., without grouping Arm A and Arm B)

Different statistical models for the bleed rate:

- An alternative NB modeling approach (using the GENMOD procedure) for the primary endpoint in which the A versus C and B versus C randomized comparisons are tested using separate models, including in the first model only the data for patients randomized into arms A and C and in the second model only the data for patients randomized into arms B and C.
- Analysis of variance (ANOVA)
- Van Elteren test (calculated ABR)

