6. STATISTICAL CONSIDERATIONS AND ANALYSIS PLAN

6.1 DETERMINATION OF SAMPLE SIZE

The sample size for this study is based on clinical rather than statistical considerations, taking into account the limited number of patients with hemophilia A without inhibitors available for participation in clinical studies and in an effort to collect sufficient data to assess the safety and efficacy of emicizumab.

The sample size calculation is based on the evaluation of the primary efficacy endpoint, defined as the number of bleeds over time (i.e., bleed rate) with emicizumab (treatment group, λ_t) versus no prophylaxis (control group, λ_c), which are said to follow a negative binomial (NB) distribution. With consideration of enrollment feasibility, a sample size of 75 patients, assuming an allocation ratio of 2:2:1 (30 patients in each randomized treatment group and 15 patients in control group), will achieve a power of more than 90% assuming a mean ABR of 4 and 14 bleeds (with variances = mean \times 10) for the emicizumab treatment and control arms respectively, representing an expected 71% reduction in the ABR compared to the control arm. Initial sample size calculations were performed with East[®], Version 6 (Cytel, Cambridge, MA), assuming the patients from each treatment group are followed up to 0.5 units of time (i.e., 24 weeks).

However, the above approach to sample size calculation assumes similar follow-up for each patient. Because this is unlikely to be seen in the study, power was also estimated by simulation to account for different follow-up times among patients. Conducting simulations on the basis of an NB regression model including an offset variable to account for variable follow-up times, with all other assumptions remaining the same as

previously described, the sample size is projected to have greater than 90% power at the 2-sided 0.05 level of significance.

The analysis will include all enrolled patients regardless of their length of follow-up. Therefore, to ensure the analysis is based on sufficient follow-up data and with 2:2:1 treatment to control randomization, approximately 34 patients in each randomized emicizumab treatment arm (68 in total) and 17 patients in the control arm (approximately 85 patients in total) will be enrolled.

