## **2.4 DETERMINATION OF SAMPLE SIZE**

The sample size for this study is based on clinical rather than statistical considerations, taking into account the limited number of patients with hemophilia A without inhibitors available for participation in clinical studies and in an effort to collect sufficient data to assess the safety and efficacy of emicizumab.

The sample size calculation is based on the evaluation of the primary efficacy endpoint, defined as the number of bleeds over time (i.e., bleed rate) with emicizumab (treatment group,  $\lambda_t$ ) versus no prophylaxis (control group,  $\lambda_c$ ), which are said to follow a negative binomial (NB) distribution. With consideration of enrollment feasibility, a sample size of 75 patients, assuming an allocation ratio of 2:2:1 (30 patients in each randomized treatment group and 15 patients in control group), will achieve a power of more than 90% assuming a mean ABR of 4 and 14 bleeds (with variances = mean  $\times$  10) for the emicizumab treatment and control arms respectively, representing an expected 71% reduction in the ABR compared to the control arm. Initial sample size calculations were performed with East®, Version 6 (Cytel, Cambridge, MA), assuming the patients from each treatment group are followed up to 0.5 units of time (i.e., 24 weeks).

However, the above approach to sample size calculation assumes similar follow-up for each patient. Because this is unlikely to be seen in the study, power was also estimated by simulation to account for different follow-up times among patients. Conducting simulations on the basis of an NB regression model including an offset variable to account for variable follow-up times, with all other assumptions remaining the same as previously described, the sample size is projected to have greater than 90% power at the 2-sided 0.05 level of significance.

The analysis will include all enrolled patients regardless of their length of follow-up. Therefore, to ensure the analysis is based on sufficient follow-up data and with 2:2:1 treatment to control randomization, approximately 34 patients in each randomized

[figure not shown]

emicizumab treatment arm (68 in total) and 17 patients in the control arm (approximately 85 patients in total) will be enrolled.

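### SAP 4.5.4 lists an unqualified ANOVA for the bleed rate; run in the ordinary way on calculated ABR, it would understate the standard error of A-C and B-C by about 25% under the plan's own variances

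*SAP*

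**What the plan says.** SAP 4.5.4, under "Different statistical models for the bleed rate", names three checks on the primary analysis: negative binomial (NB) models fitted separately for A vs C and B vs C, ANOVA, and the Van Elteren test. The ANOVA entry reads only "Analysis of variance (ANOVA"). It gives no response scale, number of arms, covariates, contrast or variance structure. The Van Elteren entry does name its response, calculated ABR.

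Two other places suggest how the ANOVA would be set up. The primary NB model (SAP 4.5.1) and the quality-of-life ANOVA (SAP 4.5.2.5) each use one model with a three-level treatment effect. On the other hand, SAP 4.5.1 runs the Van Elteren test pair by pair.

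The variance assumption is in SAP 2.4: "a mean ABR of 4 and 14 bleeds (with variances = mean" multiplied by 10). Planned enrolment, in Protocol 6.1, is "approximately 34 patients in each randomized emicizumab treatment arm (68 in total) and 17 patients in the control arm".

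**The concern.** Ordinary ANOVA assumes the same residual variance in every arm. The plan's sizing assumption says otherwise: the variance rises with the mean, so the control arm has the largest variance and, under 2:2:1 allocation, the fewest patients. The pooled variance is then driven mainly by the 68 emicizumab patients, and the standard error of a comparison with control comes out too small.

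A sensitivity analysis is there to show whether the primary result holds under other assumptions. This one could report the ABR difference more precisely than the plan's own variances allow.

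**Working it through.** **Inputs.** ABR 4 (emicizumab) and 14 (control), with variance 10 times the mean, so 40 and 140 (SAP 2.4). Arms of 34, 34 and 17 (Protocol 6.1, SAP 2.4). Control follow-up ends at the switch, allowed after 24 weeks (SAP 2.3.1.1 and 4.1). Emicizumab follow-up is 6 to 12 months or longer (Protocol 3.3.4), with no distribution stated.

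**The plan's own figure first.** SAP 2.4 states that "30 patients in each randomized treatment group and 15 patients in control group" "will achieve a power of more than 90" per cent, with patients "followed up to 0.5 units of time (i.e., 24 weeks"). For NB counts, variance = mean + k × mean², so variance = 10 × mean gives k = 9/mean: 2.25 for emicizumab and 0.643 for control.

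- Variance of the log rate ratio = (1/(4 × 0.5) + 2.25)/30 + (1/(14 × 0.5) + 0.643)/15 = 0.0917 + 0.0524 = 0.144, so SE = 0.380.
- ln(14/4) = 1.253, and 1.253/0.380 = 3.30.
- Power = Φ(3.30 − 1.96) = 0.91.

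This agrees with the plan, so the variances are being read as intended.

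**Standard error of A-C (B-C is identical).**

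- True: √(40/34 + 140/17) = √9.41 = 3.07.
- Three-arm pooled variance: (33 × 40 + 33 × 40 + 16 × 140)/82 = 59.5. Model SE: √(59.5 × (1/34 + 1/17)) = √5.25 = 2.29. Ratio to the true SE: 0.75.
- Two-arm pooled variance (A and C only): (33 × 40 + 16 × 140)/49 = 72.7. Model SE: √(72.7 × (1/34 + 1/17)) = 2.53. Ratio: 0.83.

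With these ratios, the large-sample coverage of a nominal 95% interval is 86.3% for three arms and 90.3% for two.

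**Simulated coverage of the true difference, −10.** Counts are NB with the dispersions above, converted to untransformed ABR, with 20,000 to 200,000 trials per setting.

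| Setting | Pooled variance | Separate variances (Welch) |
|---|---|---|
| Three arms, equal follow-up | 84.9-85.3% | 93.4-93.6% |
| Three arms, control 24 weeks, emicizumab uniform 24-52 weeks (assumed) | 84.4-84.7% | 93.2-93.6% |
| Two arms, equal or unequal follow-up | 88.1-88.9% | about 93.5% |
| Three arms plus stratum term, stratum rate ratio 1 to 3 (assumed) | 85.2-89.3% | not simulated |
| Three arms, normal data with variances 40 and 140 | 85.6% | 95.0% |
| Three arms, equal rates (both 14 or both 4), equal follow-up | 95.1-95.3% | – |

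The last row is the null case. Equal means imply equal variances under the plan's rule, and the pooled interval then has its nominal coverage.

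**Width of the corrected interval.** Satterthwaite degrees of freedom at the plan values are 9.41²/((40/34)²/33 + (140/17)²/16) = 88.6/4.28, about 20.7. The t quantile is about 2.08, against 1.99 on 82 degrees of freedom. Relative width is (3.07 × 2.08)/(2.29 × 1.99), about 1.40. Simulated average widths agree (38-40% wider).

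**The case against.** The strongest reply is that the SAP does not commit to the analysis that produces these figures. It names no response scale and no number of arms, and the result depends on both. Pair-by-pair models would be a reasonable reading, given the entry directly above and the Van Elteren rule in SAP 4.5.1, and they give about 88-89%. On log(ABR + 1) the problem disappears: simulated variances are about 1.15 (emicizumab) and 0.99 (control), and the pooled standard error is 2-4% too large. This stands. The figure of about 85% is conditional on untransformed ABR, three arms and no strong stratum effect. It is not a property of the plan as written.

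Three stronger inferences are tempting, and the documents support none of them.

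- *A too-narrow interval will be reported.* SAP 4.5.4 promises neither an interval nor an ABR difference from the ANOVA. The 95% intervals in SAP 4.5.1 are for the primary bleed rates and rate ratio. The same standard error would, however, underlie any test or estimate that the ANOVA produces.
- *The false-positive rate is inflated.* It is not under the plan's variance rule. With both ABRs at 14, pooled ANOVA rejects in 4.9% of trials with equal follow-up and 5.2% with unequal follow-up.
- *The primary conclusion is at risk.* The ANOVA is outside the hierarchy in SAP 4.5.2, and the primary NB model does not use this residual variance. Nor do the other two checks on the list assume a common residual variance. At the plan values pooled ANOVA rejects in about 96-97% of trials and Welch in about 91-92%, so the decision would seldom differ.

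What remains is that every untransformed-ABR version with a pooled variance, under the assumed effect, covers less than 95%, and the SAP does not rule that version out.

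**Conclusion.** The point holds in conditional form and is minor. If the listed ANOVA is run in the ordinary way on untransformed calculated ABR, its equal-variance assumption conflicts with SAP 2.4. The standard error for A-C and B-C is then about 25% too small in a three-arm model, or about 17% in a two-arm model (ratio 0.83). A nominal 95% interval would cover about 85% with three arms, about 84.5% if emicizumab follow-up is assumed uniform over 24-52 weeks, about 88-89% with two arms, and 85-89% with a stratum term. All of this rests on ABRs of 4 and 14, variances of 40 and 140, and arms of 34, 34 and 17. The defect is overstated precision under the assumed effect, confined to one sensitivity analysis.

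**What to change.** In SAP 4.5.4, replace the ANOVA entry with a specified analysis: a linear model of calculated ABR, comparing A vs C and B vs C, with the randomisation stratum (<9 or ≥9 bleeds) as a covariate, a separate residual variance for each arm (for example a mixed-model GROUP=arm option) and Satterthwaite degrees of freedom. State whether the ABR difference will be reported with a 95% interval. Keeping the stratum matches the primary model; a plain Welch comparison would drop it.

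The cost is one SAP entry and one procedure option. The interval will be about 40% wider than the pooled one. Coverage improves to about 93.5%, not 95%, because the counts are skewed and there are only 17 controls. That coverage figure was simulated without the stratum term. The primary NB analysis and the hierarchy are unchanged.

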#### **4.5.5 Subgroup Analyses**

Comparative subgroup analyses describing the primary endpoint, treated bleed rate, will be conducted for the randomized portion of the study. In addition, estimated ABR including 95% CI will be calculated for all treatment arms in each subgroup. Note, due to the small sample size, all subgroup analyses will be highly sensitive to variability caused by individual patients and need to be interpreted with caution. No p-values will be calculated.

The pre-specified subgroups are:

- Age: < 18, ≥ 18
- Age: < 65, ≥ 65
- Race: Asian, Black or African American, White, Other
- Number of bleeds during 24 weeks prior to study entry: ≤ 9, > 9

- Number of target joints: no target joint, any target joint

Subgroup analyses are subject to having sufficient patients in a subgroup to provide meaningful results.

In addition, region- and/or country-specific analyses will be performed to support regulatory submissions as needed.

#### **4.6 PHARMACOKINETIC ANALYSES**

For all patients, pre-dose (trough) plasma concentrations of emicizumab will be presented descriptively by treatment arm, including arithmetic and geometric means, median, range, standard deviations, and coefficients of variation.

Nonlinear mixed effects modeling will be used to analyze the dose-concentration-time data of emicizumab following SC administration. Population PK parameters, such as clearance and volume of distribution, will be estimated, and the influence of various covariates, such as age, and body weight, on these parameters will be investigated graphically. Secondary PK parameters, such as area under the concentration-time curve (AUC), will be derived from individual post-hoc predictions. Data may be pooled with data from other studies. These analyses will be reported in a dedicated report.

In addition, region- and/or country-specific analyses will be performed to support regulatory submission as needed.

#### **4.7 SAFETY ANALYSES**

Safety will be assessed through descriptive summaries of adverse events, laboratory test results (serum chemistry and hematology, including complete blood count with differential), ECGs, vital signs, and antibodies to emicizumab and FVIII.

##### **4.7.1 Exposure to Study Medication**

Information on study drug administration will be summarized by duration and cumulative dose. In addition, treatment exposure will be summarized, including delays and interruptions. The number of patients whose dose was up-titrated will be summarized.

Patient withdrawals from study treatment will be reported in patient listings and summary tables.

##### **4.7.2 Adverse Events**

Adverse events will be summarized and presented by System Organ Class mapped term, appropriate thesaurus level, and toxicity grade (WHO Criteria) for each treatment arm. All adverse events will be coded using the current version of MedDRA at time of database closure. The total number and percentage of patients with at least one adverse event and total number of adverse events will be summarized. Separate

adverse event summaries for serious adverse events, adverse events of special interest, severity, relatedness, and discontinuation/modification will be provided.

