2.2 SAFETY OBJECTIVE

The safety objective for this study is to evaluate the overall safety of prophylactic emicizumab compared with no prophylaxis in patients with hemophilia A without inhibitors on the basis of the following endpoints:

- Incidence and severity of adverse events
- Incidence and severity of thromboembolic events
- Changes in physical examination findings and vital signs
- Incidence of laboratory abnormalities
- Incidence and severity of injection-site reactions
- Incidence of adverse events leading to drug discontinuation
- Incidence of severe hypersensitivity, anaphylaxis, or anaphylactoid reactions
- Incidence and severity of thrombotic microangiopathy
- Incidence and clinical significance of anti-emicizumab antibodies
- Incidence of de novo development of FVIII inhibitors in patients receiving emicizumab prophylaxis

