To avoid bleeds before adequate emicizumab plasma concentration is reached, these patients will continue their regular FVIII prophylaxis until the second emicizumab loading dose. At the end of the first week of treatment, 95% of patients are expected to achieve emicizumab level of 8 µg/mL, which is projected to have FVIII activity equivalent to approximately >2%. Thrombotic events were not found in the Japanese Phase I/II study where doses of FVIII were administered to treat breakthrough bleeds while patients had higher emicizumab steady-state level, supporting the safety of this approach. Importantly, routine prophylaxis will be prohibited for all patients enrolled in Arms A, B, or C and for patients in Arm D immediately after the second emicizumab dose.

Study enrollment will take place at the Week 1 visit. A patient who fulfills the inclusion and exclusion criteria should be enrolled and assigned to a treatment arm at the Week 1 visit, the same day when the first dose of emicizumab is due for patients in Arms A, B, and D.

[figure not shown]
Emicizumab is intended for prophylactic use only (i.e., not to treat bleeds that have already occurred). The primary efficacy analysis, defined as comparing the number of bleeds over time for patients randomized to receive prophylactic emicizumab versus no prophylaxis will be conducted at the earliest timepoint when all randomized patients (Arms A, B, or C) and a minimum of 40 patients from Arm D have either completed 24 weeks in the study or discontinued from the study. Therefore, there will be a range of observation periods from 6 to approximately 12 months, or longer. Study patients will be enrolled globally from the Americas, Europe, Africa, and Asia-Pacific region.

To obtain additional safety and efficacy data on emicizumab, patients who are randomized to the no prophylaxis arm (control arm, Arm C) will be expected to switch after 24 weeks to receive emicizumab prophylaxis at 3 mg/kg/2wks maintenance dose after 4 weeks of 3 mg/kg/wk loading dose. This dose was chosen to enhance the safety and efficacy data obtained with Arm B patients.

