6.6 SAFETY ANALYSES

The safety analyses population will be based on all enrolled patients grouped according to the actual treatment received. For Arm C patients, all safety data reported up to the day prior to switching will be included in the 'control arm' safety summaries, and all safety data reported on or after the date of switching to active treatment will be reported separately.

Safety will be assessed through descriptive summaries of adverse events, laboratory test results (serum chemistry and hematology, including complete blood count with differential), ECGs, vital signs, and antibodies to emicizumab and FVIII.

To evaluate the overall safety of prophylactic emicizumab compared to no prophylaxis, the incidence of adverse events will be summarized and presented by System Organ Class mapped term, appropriate thesaurus level, and toxicity grade for each treatment arm.

For clinical laboratory data, summary statistics will be presented by treatment arm. In addition, shift tables describing changes from baseline will be presented using the WHO toxicity grading scale.

Data on the impact of immunogenicity (anti-emicizumab antibodies) on safety, efficacy, and/or clinical pharmacology and PK will be summarized adopting standard language/terminology (Shankar et al. 2014).

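### Adverse events are to be set side by side as crude counts and percentages although control observation ends at about 24 weeks and Arms A and B run for 6 to 12 months or longer

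*SAP*

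**What the plan says.** Protocol 2.2 sets the safety objective: to "evaluate the overall safety of prophylactic emicizumab compared with no prophylaxis", with adverse event incidence first among its endpoints. Protocol 6.6 ties the analysis to that aim: "To evaluate the overall safety of prophylactic emicizumab compared to no prophylaxis, the incidence of adverse events will be summarized and presented" by treatment arm. SAP 4.1 attaches a safety analysis to the A versus C control and B versus C control outputs, and SAP 4.2.5 defines a population for it (SAF1ND, which leaves out Arm D).

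The observation periods differ by design:

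- **Control.** Under Protocol 6.6, "all safety data reported up to the day prior to switching will be included in the 'control arm' safety summaries". Protocol 3.1 says these patients "will be expected to switch after 24 weeks to receive emicizumab prophylaxis at 3 mg/kg/2wks maintenance dose".
- **Arms A and B.** Protocol 3.1 says that "there will be a range of observation periods from 6 to approximately 12 months, or longer", and Protocol 3.3.4 gives 6 to 12 months or longer for emicizumab. The only end date the SAP defines for these arms is the one for bleeds in SAP 2.3.1.1 (clinical cutoff or withdrawal, or the day before up-titration). No shorter window is given for safety.

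The planned adverse event measure is in SAP 4.7.2: "The total number and percentage of patients with at least one adverse event and total number of adverse events will be summarized". Observation time (SAP 4.3) and drug exposure (SAP 4.7.1) are summarised separately and are not used as denominators.

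**The concern.** The chance that a patient has had at least one event, and the number of events, both grow with time observed. When one arm is watched longer, a crude percentage mixes the effect of treatment with the effect of follow-up. This is the trial's only randomised safety comparison, and part of any difference in it would reflect how fast patients were enrolled, because that sets how long Arms A and B have been followed at the cutoff.

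The plan handles the same imbalance for bleeds. The negative binomial model carries follow-up time as an offset (SAP 4.5.1), and one sensitivity analysis uses only the first 24 weeks (SAP 4.5.4). Adverse events get neither.

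**Working it through.** **The plan's own safety figure.** SAP 2.4 gives a probability of 0.66 to 0.72 of observing an event of 1% true incidence among 108 to 128 emicizumab patients (34 + 34 + 40 and 34 + 34 + 60).

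- 1 − 0.99^108 = 0.662
- 1 − 0.99^128 = 0.724

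The figure is reproduced. It treats incidence as one fixed percentage per patient, without reference to time observed.

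**Inputs for the comparison**

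- Control window: 24 weeks (Protocol 3.1 and 6.6).
- Emicizumab window: 24 to 52 weeks, from the 6 to 12 months in Protocol 3.1 and 3.3.4. The even spread over that range is an assumption.
- The same constant hazard h in both arms: an assumption.
- Control 24-week risk p: not in the documents, so a range is shown.

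**Formulas**

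- Hazard per week: h = −ln(1 − p)/24.
- Crude percentage at w weeks: 1 − exp(−hw).
- Average over even follow-up from 24 to 52 weeks: 1 − [exp(−24h) − exp(−52h)]/(28h).

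Worked case, p = 30%: h = 0.3567/24 = 0.01486. Then exp(−24h) = 0.700, exp(−52h) = 0.462 and 28h = 0.416. The average is 1 − 0.238/0.416 = 0.427.

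| Control, 24 weeks | Emicizumab, even over 24–52 weeks | Ratio | Emicizumab, all at 52 weeks | Ratio |
|---|---|---|---|---|
| 10% | 15.3% | 1.53 | 20.4% | 2.04 |
| 30% | 42.7% | 1.42 | 53.8% | 1.79 |
| 50% | 65.7% | 1.31 | 77.7% | 1.55 |
| 90% | 96.5% | 1.07 | 99.3% | 1.10 |

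**Event counts per patient.** Mean follow-up under the even spread is (24 + 52)/2 = 38 weeks, so the ratio is 38/24 = 1.58. If all reach 52 weeks it is 52/24 = 2.17.

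**What a single trial would show.** This was simulated with 34 emicizumab and 17 control patients, p = 30%, equal hazards and even follow-up over 24 to 52 weeks. The emicizumab arm had the higher crude percentage in 79% of trials and the lower in 16%; the rest were ties. With equal follow-up the split was 46% and 45%.

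**With the time basis equalised.** Over a common 24 weeks the p = 30% case reads 30% in both arms. As a rate it is 0.01486 × 52.18 × 100 = 77.5 first events per 100 patient-years in both arms.

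**The case against.** The strongest reply is that safety here is descriptive (SAP 4.7). No test or decision rule depends on these tables, and the distortion runs against emicizumab, so it does not hide harm. This is true and it limits the consequence. Even so, Protocol 6.6 offers these summaries as the evaluation against no prophylaxis, and side-by-side percentages can mislead without a p-value.

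Several limits on size also stand:

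- Switching is expected (Protocol 3.1) or an opportunity (SAP 2), not compulsory. A control patient who stays on no prophylaxis goes on contributing control time.
- Up-titration in Arms A and B is possible from Week 25 (Protocol 4.3.2), and data on the higher dose are reported separately (SAP 4.1). For those patients the initial-dose window may end close to the control window.
- Events confined to the first weeks give a ratio near 1, and near-universal events meet a ceiling.

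Four stronger readings are tempting, and the documents do not support them:

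- **That a true difference cannot be recovered.** Observation time (SAP 4.3), exposure (SAP 4.7.1) and event totals (SAP 4.7.2) let a reader form a crude rate. What is missing is a prespecified rate with an interval.
- **That emicizumab is bound to look worse.** The bias holds on average; with 17 controls one trial can go the other way.
- **That visit frequency is part of the same fault.** Arms A and B have 10 visits with an adverse event entry through Week 21, against 6 in Arm C. Events are also captured as they occur (Protocol 3.1), and the extra visits fall inside the first 24 weeks, so equalising follow-up would not correct for them.
- **That days hospitalised suffer likewise.** SAP 4.5.3 does not say over what period they are totalled, so no flaw is shown.

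**Conclusion.** The concern holds as a tendency in descriptive tables. As planned, the randomised adverse event comparison is confounded with length of observation, and at equal risk the emicizumab arms would tend to show higher percentages and counts. On the assumptions above, the crude percentage would be inflated by a factor of about 1.3 to 1.5 for control risks of 10% to 50%, and events per patient by about 1.6, or 2.2 at the upper end. These sizes rest on constant equal hazards and an assumed spread of follow-up, and the limits conceded above make the gap smaller. At later data cuts it would grow, because control time stays near 24 weeks while emicizumab time accrues. The bleed analyses are not affected. The change should be made, since the bias follows from the plan as written and is cheap to remove.

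**What to change.** In SAP 4.7.2, for SAF1ND (Arms A, B and C control), add:

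1. Adverse event tables restricted to the first 24 weeks in every arm. These run from the Week 1 visit to the day before Week 25 dosing or switch, or to withdrawal if earlier. A control patient who switches late or not at all is cut at the same 24-week point.
2. Adverse event rates per patient-year with 95% CIs over each arm's full follow-up.

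Both are useful. The 24-week table does not depend on a constant hazard. The rate uses all the data, but needs care for events that cluster early, because longer follow-up dilutes them. Keep the all-data tables and label them descriptive long-term safety.

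The cost is a few lines of SAP text and a small amount of extra table programming: a date filter and a person-time denominator. No new data are needed.
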